9.4. Data Sources

9.4.1. The UK Clinical Practice Research Datalink General Practitioner OnLine database (CPRD GOLD)

The CPRD GOLD is the world's largest computerised database of linked anonymised longitudinal medical records from primary care. The data are drawn from the computer systems used by general practitioners (GPs) to maintain the clinical records within their practices. As of March 2011, CPRD GOLD contains records from over 12 million patients contributing 64 million person-years of prospectively recorded high-quality primary healthcare data [Williams, 2012].

The CPRD GOLD is operated on a non-profit basis by the UK Medicines and Healthcare products Regulatory Agency (MHRA), containing coded longitudinal medical records from general practices and more recently from hospital-based care (e.g., Hospital Episode Statistics, HES). The current linkage between CPRD GOLD primary care data and HES data is around 50% as of Q1 2013. The CPRD GOLD database is licensed in-house by GSK. Data quality is monitored continuously by the MHRA and practices that fail to maintain the required standards are removed from the database.

The latest update provided by the CPRD GOLD team in Q1 of 2013 (first release of 2013) contains data for 10,960,947 research standard patients, drawn from 660 practices throughout the UK. A total of 4,727,669 patients from 548 practices are currently active in the database. The CPRD GOLD population closely matches the age and gender distribution of the UK population as a whole. Mean follow-up is 6.9 years (median 5.0 years). Recorded data include demographic information, prescription details, clinical events, preventive care provided, specialist referrals, hospital admissions and their major outcomes. Data are retrieved by means of the READ classification system; READ codes are a coded thesaurus of clinical terms, which are the basic means by which clinicians record patient findings and procedures in health and social care IT systems across primary and secondary care (e.g. GP surgeries and pathology reporting of results). The Medcodes are the abbreviated terms which mean CPRD GOLD medical codes. Medcodes consisting of READ codes are used to enter medical diagnosis in the CPRD GOLD database.

9.4.2. Data source for case ascertainment

First, the CPRD GOLD is based on data from GPs, while most auto-immune diseases would probably be diagnosed in specialist settings. Consequently, the number of auto-immune diseases, the quality of the information, and the diagnostic certainty might be lower compared to other databases that include hospital data only. In particular the specific information related to the onset of clinical symptoms, and radiological and biological data associated with the etiologic diagnosis of auto-immune diseases may not all be available in the CPRD GOLD database and associated resources. Besides, not all general practices participating to CPRD GOLD have consented to the linkage between CPRD GOLD primary care data and HES data (current linkage around 50% as of Q3 2012). Specific algorithms for each outcome of interest have been developed (Annex 5)

116239 (EPI-HPV-040 VS UK) Protocol FDA - EMA PASS Final Version 1

and available "free text" that is related to auto-immune disease diagnosis will be requested from CPRD GOLD, when needed.

Moreover, in a recent study by [Chao & Jacobsen, 2012], the authors recommended that expert case review of medical records is used in autoimmune safety studies, and case identification can be expanded by use of laboratory test results and other relevant measures in addition to specific ICD-10 diagnosis codes.

[figure not shown]
The ascertainment of the etiologic diagnosis and date of disease onset for all identified auto-immune diseases will be performed by a contract research organisation (CRO) to ensure the correct classification of each case. The CRO will review all subject data retrieved from CPRD GOLD including medcodes (including clinical, laboratory, and treatment files), the relevant "free text" and HES (including specific ICD-10 diagnostic codes), when available. They will assess whether the aetiology of the auto-immune disease is confirmed or not and whether the date of disease onset falls within the observation period of the study, which is one year after the reference date.

[figure not shown]
In the event that the aetiology or the date of onset could not be confirmed, a second review step will be conducted with an expert physician panel to reach an agreement about the case ascertainment, and, if they cannot reach an agreement, then the different clinical opinion of the experts will be listed. The experts will be blinded with regards to HPV vaccine exposure.

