9.3. Variables

9.3.1. Primary endpoint

• Occurrence of new onset of confirmed⁴ autoimmune disease during the period of one year following administration of the first dose of Cervarix (risk period) among an exposed cohort and during an equivalent time period in the unexposed cohorts for the following two co-primary composite endpoints:

[1] Neuroinflammatory/ophthalmic autoimmune diseases:

- Multiple Sclerosis
- Transverse myelitis
- Optic neuritis
- Guillain-Barré syndrome, including Miller Fisher syndrome and other variants
- Other demyelinating diseases:
 - Acute disseminated encephalomyelitis, including site specific variants: e.g. non-infectious encephalitis, encephalomyelitis, myelitis, myeloradiculomyelitis
 - AI peripheral neuropathies and plexopathies (including chronic inflammatory demyelinating polyneuropathy, multifocal motor neuropathy and polyneuropathies associated with monoclonalgammopathy).
- Auto-immune uveitis

[2] Other autoimmune diseases:

- Systemic lupus erythematous
 - Autoimmune (AI) disease with rheumatologic conditions:
 Rheumatoid arthritis (RA)

⁴ Auto-immune disease diagnosis ascertainment by an expert physician panel (Section 9.4.2).

- Juvenile rheumatoid arthritis (JRA)
- Still's disease
- Psoriatic arthritis
- Ankylosing Spondylitis
- AI haematological conditions:
 - Idiopathic thrombocytopenic purpura (ITP)
 - AI haemolytic anaemia
- AI endocrine conditions:
 - Type 1 diabetes mellitus
 - AI thyroiditis including Hashimoto's disease, Graves' /Basedows' disease
- Inflammatory bowel / hepatic diseases:
 - Crohn's diseases
 - Ulcerative colitis
 - Autoimmune hepatitis

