9.3.3.2. Clinical outcomes

Occurrence of auto-immune diseases defined as study endpoints will be identified using defined algorithms (see Annex 5).

For each case, the following data will be extracted:

- Medcode(s)
- Date of event

The associated "free text" (event text ID) if any will be identified. For all the identified cases of auto-immune diseases, the associated free text will be reviewed by a GSK-identified reviewer for confirmation and determination of the date of first symptoms of NOAD.

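### Blinding to HPV vaccine exposure is stated only for the second-step expert panel, not for the reviewers who can confirm cases and date onset, and the text does not protect it against unmasking by dates

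*Protocol*

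**What the plan says.** The protocol describes case confirmation in four places.

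- **Endpoint definition (9.3.1 footnote 4; the same idea in Abstract footnote 1).** A confirmed case means "Auto-immune disease diagnosis ascertainment by an expert physician panel".
- **First review step (9.4.2).** "The ascertainment of the etiologic diagnosis and date of disease onset for all identified auto-immune diseases will be performed by a contract research organisation". On the material used: "The CRO will review all subject data retrieved from CPRD GOLD including medcodes", together with free text and HES where available. The CRO decides whether the aetiology is confirmed and "whether the date of disease onset falls within the observation period of the study, which is one year after the reference date".
- **Second review step (9.4.2).** Only where aetiology or onset date remains unconfirmed does the protocol provide that "a second review step will be conducted with an expert physician panel". The blinding statement closes that paragraph: "The experts will be blinded with regards to HPV vaccine exposure".
- **Free-text review (9.3.3.2 and 9.6.1).** For all identified cases, "the associated free text will be reviewed by a GSK-identified reviewer for confirmation and determination of the date of first symptoms of NOAD". Section 9.6.1 has this reviewer enter the free-text findings and the final classification.

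No blinding is stated for the CRO or for the sponsor-identified reviewer. The Abstract says that an independent entity abstracts the validation material, but independence is not blinding. The protocol does not say whether reference dates, calendar dates or immunisation entries are removed from the files given to any reviewer.

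**The concern.** Confirming an autoimmune diagnosis and dating its first symptoms are both matters of judgement here. Section 9.4.2 itself concedes that onset, radiological and biological information may be missing from primary-care records. Blinding is what keeps such judgements unrelated to exposure.

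Section 9.9 relies on that without saying so. It states that poor specificity biases the risk ratio towards the null and that poor sensitivity does not bias it for a rare event. Both statements hold only if the errors do not depend on exposure.

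The protocol raises blinding but limits it to one step, and that step handles only the cases left unresolved. At stake are the case counts in both co-primary composites and, through the onset date, the allocation of events to periods in the self-control case-series (SCCS).

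**Working it through.** **1. Who decides, and who is stated to be blinded**

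| Party | Decides | Blinding stated? |
|---|---|---|
| CRO (9.4.2) | Aetiology and onset date, all identified cases | No |
| Sponsor-identified reviewer (9.3.3.2, 9.6.1) | Confirmation and first-symptom date; enters final classification | No |
| Expert panel (9.4.2) | Cases unresolved at step 1 | Yes |
| Expert panel as credited in footnotes 1 and 4 | Diagnosis, with no limit to unresolved cases | – |

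The last row does not agree with the first two.

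**2. What the dates reveal**

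- Reference date in the exposed cohort: date of the first Cervarix dose (9.1.2), between 1 September 2008 and 31 August 2010 (9.2.4.1). Follow-up starts no earlier than 1 September 2008.
- Reference date in historical females: between 1 September 2005 and 31 August 2007 (9.2.4.2). Adding 12 months (9.7.5.1), follow-up ends by about 31 August 2008.
- The two windows do not overlap. For a female case, the reference date, or an onset date known to lie in the follow-up window, fixes the cohort. This applies to the panel as much as to the CRO.

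**3. Whether the planned male comparison removes the bias**

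Let k be the ratio of confirmation probability, exposed to historical females, and t a change over time shared by both sexes. With no vaccine effect:

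- female log rate ratio = ln k + ln t
- male log rate ratio (concurrent vs historical, both unexposed) = ln t
- adjusted effect in 9.7.9.1 = (ln k + ln t) − ln t = ln k

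The adjustment removes the period effect and leaves k. Under 9.7.5.1 it is applied only if the male cohorts differ significantly.

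**4. Illustration of size**

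The protocol has no figure on this point to reproduce. Assumptions: true rate ratio 1; 65,000 person-years per cohort (a full year for all 65,000 subjects, so an upper figure); background rates per 100,000 from 9.5.1; two-sided Wald test at 0.05; and the value of k, which is not in the documents.

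Expected cases: m0 = 65,000 × rate and m1 = k × m0. Then d = ln k / √(1/m1 + 1/m0), and P(reject) = Φ(d − 1.96) + Φ(−d − 1.96).

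Example with rate 100 per 100,000 and k = 1.2: m0 = 65, m1 = 78, d = 0.182/0.168 = 1.09, P = 19.2%.

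| Rate per 100,000 | k = 1.1 | k = 1.2 | k = 1.3 |
|---|---|---|---|
| 10 (neuroinflammatory, upper figure in 9.5.1) | 5.4% | 6.4% | 7.9% |
| 50 (other NOAD) | 6.8% | 12.0% | 20.3% |
| 100 (other NOAD) | 8.6% | 19.2% | 35.6% |

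If only step 1 is affected, at k = 1.2, and it settles a share s of cases, the spurious rate ratio is 1.2s + (1 − s). This gives 1.10, 1.14 and 1.18 for s = 50%, 70% and 90%. The protocol does not give s. With k below 1 the bias runs downwards and could hide a real excess.

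**The case against.** The strongest reply is that silence is not disclosure. Several stronger readings are tempting, and the documents do not support them.

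- **That first-step reviewers are shown vaccine exposure.** No section says so. The files that 9.4.2 names are clinical, laboratory and treatment files, free text and HES; the immunisation file in 9.3.3.1 is not named. Every cohort has a reference date, and in three of the four it is randomly assigned (9.2.2). What stands is that nothing excludes disclosure and that the CRO's task uses the reference date.
- **That step 1 confirms most cases.** The protocol gives about 280 cases to review (9.9) and no split between steps.
- **That any dated record gives the cohort away.** It does not. Exposed girls need at least 12 months of prior record, so their files hold entries from 2007–08 or earlier, which overlap with historical follow-up. An onset before the reference date in that period is not identifying by itself.
- **That the 31–40% confirmation range in the study cited in section 7 measures the bias.** Nothing links that range to exposure or blinding.

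In the SCCS every case is vaccinated, so confirmation cannot differ between exposed and unexposed subjects. What remains there is the dating of onset, and the six-month buffer makes it less likely that an event moves directly between risk and control time. Section 9.9 already lists onset dating as a limitation. Annex 5 or a review charter, neither shown, may contain masking rules, and hiding the calendar period completely in free text and HES may not be feasible.

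These points narrow the concern but do not remove it. The protocol itself states blinding and restricts it to one step.

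**Conclusion.** The concern holds in a limited form. Blinding is stated only for the second-step panel. The parties who can confirm cases and date onset without the panel are not stated to be blinded, and the CRO is asked to use a date that is the vaccination date in exposed subjects. Because the female follow-up windows do not overlap, the text does not secure even the panel's blinding. Separately, the protocol gives three accounts of who confirms a primary-endpoint case.

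The size of any bias is unknown and it could go either way. Under the assumed ratios of 1.1 to 1.3 it is small for the neuroinflammatory composite (at most 7.9% false significance at 10 per 100,000) and larger for the other composite (up to 35.6% at 100 per 100,000). The male-cohort adjustment would not remove it. The conclusion does not depend on those ratios: it rests on the wording of 9.3.3.2 and 9.4.2 and on the calendar windows. It would fall away only if an unseen document masks the first step.

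**What to change.** In 9.3.3.2 and 9.4.2:

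- Extend blinding to every review step and every reviewer.
- Remove HPV and other immunisation entries from the case files, including mentions in free text.
- Withhold the reference date. Reviewers record diagnosis status and onset date only, and a program then assigns each case to pre-reference, risk, buffer or control time.
- Where feasible, shift each subject's dates by a subject-specific offset that keeps intervals intact. Declare any remaining unblinding by calendar period as a limitation in 9.9.
- Reconcile footnotes 1 and 4 (panel confirms) with 9.4.2 (CRO confirms, panel only for unresolved cases) and 9.3.3.2 (sponsor-identified reviewer confirms), and state whether that reviewer and the CRO are the same party.

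The cost is some programming plus manual redaction of free text and HES for about 280 cases, with no additional reviewer. It should be done before review starts: once files have been judged with exposure recognisable, only a fresh blinded review would repair the result.

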9.5. Study size

9.5.1. Sample size for cohort design

The target sample size is 50,000 subjects in each cohort. The relative risk (RR) that would be detected with 80% power and alpha = 0.05 is given in Figure 3 versus the incidence rate in the (Cervarix) unexposed cohort. The detectable difference in incidence rate (= additional cases per 100,000 person-years) is also depicted.

(Method: Comparison of two independent proportions using a likelihood ratio test, PASS 2005)

Cohorts of 50,000 subjects each should allow detection, with 80% power, of a RR between 3.7 and 18.7 for the neuro-inflammatory NOAD (incidence rate between 10 and 1/100,000 person-years) and between 1.6 and 2.0 for other NOAD (incidence rate between 100 and 50/100,000 person-years).

Because of risk of lost to follow-up, the sample size is increased by approximately 30% in each cohort to approx. 65,000 subjects.

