9.7.1. Hypotheses

9.7.1.1. Hypotheses for the cohort analysis

Null hypothesis (H0): the incidence of neuroinflammatory/ophthalmic autoimmune diseases (other autoimmune diseases) in the exposed female cohort is equal to the incidence in the historical non-exposed female cohort (historical cohort).

Alternative hypothesis (H1): the incidence of neuroinflammatory/ophthalmic autoimmune diseases (other autoimmune diseases) in the exposed female cohort is different from the incidence in the historical unexposed female cohort (historical cohort).

These hypotheses will be tested separately for each of the two co-primary endpoints. No alpha adjustment will be done.

The same hypotheses will be tested between the two male cohorts.

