9.7.8. Statistical calculations

All the statistical calculations will be done in SAS 9.2 or higher.

All the statistical tests will be two-sided at alpha level of 0.05.

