9.7.9. Statistical models

9.7.9.1. Poisson regression

Poisson regression will be computed using the SAS GENMOD procedure. The dependent variable is the number of events (*Y*). The main model (Model 1) will include the exposure status (exposed (X=1) vs. non-exposed (X=0)) as a binary independent variable, the age-group ([9-18],[18-25]) as a covariate, and the log-transformed total person-time (*PY*) of each exposed and unexposed cohort as an offset.

116239 (EPI-HPV-040 VS UK) Protocol FDA - EMA PASS Final Version 1 $\ln(Y) = \beta_0 + \beta_1 X + \beta_2 Z + \ln(PY)^\circ$

Female cohort model:

The coefficients β_1 and β_2 are the coefficients associated to exposure effect and age-group, respectively. The risk ratio (exposed/unexposed) will be derived as the exponential of the coefficient associated with the exposure status and its 95% Wald confidence interval.

The SAS code is:

PROC GENMOD data=<filename>; MODEL Y= X Z / offset=Ln_PY dist=poisson link=log; RUN;

The same model will be run for comparing the two male cohorts (concurrent vs. historical)

Male cohort model:

 $\ln(Y) = \beta_{0'} + \beta_{1'} X + \beta_{2'} Z + \ln(PY)^{\circ}$

The coefficient $\beta_{l'}$ is the time effect (concurrent vs. historical) in males.

The exposure effect in females adjusted for temporal effect in males model will be:

 $\ln(Y) = \beta_0 + \beta_{11} X_1 + \beta_{12} X_2 + \beta_{13} X_3 + \beta_2 Z + \ln(PY)^{\circ}$

Where:

 X_1 is '1' for the exposed female cohort and '0' for the other cohorts;

 X_2 is '1' for the concurrent male cohort and '0' for other cohorts;

X₃ is '1' for the historical male cohort and '0' for the other cohort.

The Cervarix effect in females adjusted for the temporal effect in males will be computed as :

$$\beta_{1*} = \beta_{11} - (\beta_{12} - \beta_{13})$$

The SAS code is:

PROC GENMOD data=<filename>; Class X (ref=' 1'); MODEL Y= X Z / offset=Ln_PY dist=poisson link=log; Contrast "vaccine adjusted effect in Females" X 1 -1 +1// estimate=exp;; RUN;

Note: X=1 for the non-exposed female cohort, 2 for the exposed female cohort, 3 for concurrent male cohort, and 4 for the historical male cohort.

Sensitivity analysis: A Poisson regression model including, in addition to the exposure and the age-group, other covariates

- Region (class variable: 13 regions defined in CPRD)
- Vaccination during the year prior to reference data (2 classes: yes, no)

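### At the low-incidence end of the neuro-inflammatory endpoint, the planned Wald interval gives about 26% power, not the 80% stated from a likelihood-ratio calculation

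*Protocol*

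**What the plan says.** Protocol section 9.5.1 sets the planning size: "The target sample size is 50,000 subjects in each cohort". It states the property claimed: "The relative risk (RR) that would be detected with 80% power and alpha = 0.05 is given in Figure 3", and then "Cohorts of 50,000 subjects each should allow detection, with 80% power, of a RR between 3.7 and 18.7 for the neuro-inflammatory NOAD". The two RRs correspond to unexposed rates of 10 and 1 per 100,000 person-years respectively. The method is given as "Comparison of two independent proportions using a likelihood ratio test, PASS 2005". For loss to follow-up, "the sample size is increased by approximately 30% in each cohort to approx. 65,000 subjects".

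Section 9.7.1.1 covers the co-primary endpoints: "These hypotheses will be tested separately for each of the two co-primary endpoints. No alpha adjustment will be done". Section 9.7.8 adds: "All the statistical tests will be two-sided at alpha level of 0.05". Neither section names a test.

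Section 9.7.9.1 fixes the model (Poisson regression in GENMOD, exposure and age group as terms, log person-time as offset) and the reported inference: "The risk ratio (exposed/unexposed) will be derived as the exponential of the coefficient associated with the exposure status and its 95% Wald confidence interval". The Model 1 code contains no option for likelihood-ratio, profile-likelihood or exact inference. The protocol does not say what happens if a cohort has no cases.

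**The concern.** The power statement and the analysis rest on different methods. With large counts this would not matter, because Wald and likelihood-ratio inference agree. Here the stated range runs down to an expected 0.5 cases in the comparator, where they do not agree at all. If the historical cohort has no cases, the log risk ratio diverges, its standard error explodes, and the Wald interval covers everything.

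At stake is one of two co-primary endpoints in a post-marketing safety study. The pattern that should raise most concern, several exposed cases and none in the comparator, would give a risk ratio with an uninformative interval.

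**Working it through.** **Inputs.** n = 50,000 per cohort, 1:1; two-sided alpha 0.05; 12 months of follow-up (section 9.7.5.1); unexposed rate 1 to 10 per 100,000; RR 18.7 to 3.7. Counts are taken as Poisson with 50,000 person-years per cohort (binomial counts agree). With person-time balanced by matching, the age term drops out: the exposure estimate is ln(y/x) with SE √(1/x + 1/y), where x is the historical and y the exposed count.

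**Step 1: the plan's own figure.** Pooled normal approximation:

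Φ{ [ (p1 − p0)√n − 1.96√(2p̄(1 − p̄)) ] / √(p0(1 − p0) + p1(1 − p1)) }

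With p0 = 0.00001, p1 = 0.000187 and p̄ = 0.0000985, this is Φ{ (0.03958 − 0.02751)/0.01403 } = Φ(0.86) = 80.5%. At 10/100,000 and RR 3.7 it gives 79.5%. The stated figures are therefore reproduced. Enumerating the likelihood-ratio test itself gives 93.8% at RR 18.7 (80% is reached at RR about 13.0), so 18.7 is conservative for the test named.

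**Step 2: what the Wald interval needs.** Fitting the planned model with the age term to 0 versus 9 cases gives SE about 14,000 and p = 0.999; the likelihood-ratio chi-square for the same data is 12.5. With one historical case, 8 exposed cases are needed: ln 8/√(1 + 1/8) = 2.0794/1.0607 = 1.9605, just above 1.95996. Seven give p = 0.069.

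**Step 3: power at 1/100,000 and RR 18.7.** Expected counts are 0.5 and 9.35.

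| Historical cases x | P(x) | Exposed cases needed | P(reached) | Product |
|---|---|---|---|---|
| 0 | 0.6065 | none suffices | 0 | 0 |
| 1 | 0.3033 | 8 | 0.7155 | 0.2170 |
| 2 | 0.0758 | 10 | 0.4586 | 0.0348 |
| 3 | 0.0126 | 11 | 0.3362 | 0.0042 |
| 4 or more | 0.0018 | 13 or more | – | 0.0002 |

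The total is 25.6% (enumerated without rounding: 0.2563).

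**Step 4: ceiling.** As RR grows without limit, Wald power tends to P(x ≥ 1) = 1 − exp(−0.5) = 39.3%. With 65,000 fully followed, the ceiling is 1 − exp(−0.65) = 47.8%, and power at RR 18.7 is 41.4%. The ceiling at 50,000 stays below 80% until the unexposed rate reaches −ln(0.2)/0.5 = 3.2 per 100,000.

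**Step 5: across the stated range.** Between the two ends the RR is the one that gives 80% by the Step 1 formula; at the ends it is the protocol's own.

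| Rate per 100,000 | P(no historical case) | RR | Wald | Exact conditional |
|---|---|---|---|---|
| 1 | 60.7% | 18.7 | 25.6% | 80.3% |
| 2 | 36.8% | 10.5 | 44.7% | 78.9% |
| 3 | 22.3% | 7.78 | 58.2% | 78.4% |
| 5 | 8.2% | 5.53 | 72.7% | 77.9% |
| 7 | 3.0% | 4.52 | 78.3% | 77.7% |
| 10 | 0.7% | 3.7 | 80.3% | 76.4% |

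**Step 6: alternatives.** The exact conditional test treats y as Binomial(x + y, 0.5) and doubles the smaller tail. With x = 0 it rejects from y = 6 (p = 2 × 0.5⁶ = 0.031). For 0 versus 9 its lower 95% limit is q/(1 − q) with q = 0.025^(1/9) = 0.664, so RR of at least 1.97 with no upper limit. At 10/100,000 it has 76.4% power at RR 3.7 and 80.0% at RR 3.85.

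The asymptotic likelihood-ratio test rejects already at 0 versus 3 (chi-square 2 × 3 × ln 2 = 4.16, exact p = 0.25). Its enumerated type I error is 8.8% at 3/100,000, 9.7% at 4, 9.4% at 5 and 7.1% at 10.

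**The case against.** Several points on the other side stand.

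- The protocol names Wald for the interval only. A reader might infer that it prescribes a Wald test; it does not. The test is inferred from the Model 1 code, and a statistical analysis plan that is not shown could name another. The interval, however, is fixed in the protocol. Even with a likelihood-ratio p-value, the reported interval would be unusable with no comparator cases and would contradict that p-value.
- A reader might infer that 18.7 is a miscalculation. It is not: it is reproduced under a standard formula and is conservative for the test named. The fault is that the analysis does not deliver it.
- 1/100,000 may be pessimistic. Table 1 gives US female rates at ages 9 to 26 of 2.5 (multiple sclerosis), 3.9 (optic neuritis) and 11.9 (uveitis), which sum to 18.3. If the composite runs near that level, the problem does not arise. But UK rates for the latter two are not available, the UK female multiple sclerosis rate at 15 to 19 is 0.9, section 9.4.2 warns that case numbers and diagnostic certainty might be lower in this database, and section 9.5.1 itself makes the claim at 1/100,000.
- A reader might infer that a cluster of exposed cases would go unseen. The documents do not support that: the incidence difference (section 9.7.5.1) stays finite, all cases are listed (9.7.8.2), and the case-series and scan analyses (9.7.9.2, 9.7.9.3) do not use the historical count.
- Section 9.7.6 fits its Poisson model only with more than 10 cases in the exposed and unexposed female cohorts. Read per cohort, that excludes zero counts.

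**Conclusion.** Wrong as written, at the low-incidence end only. For the interval the protocol specifies, the 80% stated at 1/100,000 and RR 18.7 is about 26%, and no RR can bring it above 39%. Using all 65,000 does not rescue it. The gap narrows steadily and has closed by 10/100,000, so it would be wrong to say that the whole 3.7 to 18.7 statement fails.

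This rests on three assumptions: significance is judged by whether the Wald interval excludes 1 (or by the equivalent Wald test), person-time is balanced between the female cohorts, and a zero count in either cohort is treated as not significant. The fitted 0 versus 9 example confirms the last of these.

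**What to change.** In section 9.7.9.1, for the co-primary cohort comparison, replace the Wald interval and test with the exact conditional Poisson test and interval, stratified by age group. State that a one-sided finite bound is reported when a cohort has no cases. Fix this before outcomes are seen.

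Restate section 9.5.1 for that method: RR 18.7 at 1/100,000 stands (80.3%), and RR 3.7 at 10/100,000 becomes about 3.85. If the method also covers the other NOAD endpoint, its detectable RRs are 2.0 at 50/100,000 and about 1.66 at 100/100,000.

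Do not simply switch to the asymptotic likelihood-ratio test to match section 9.5.1. If it is kept, its inflated type I error at these counts has to be stated. Section 9.7.6 needs no change, given its case-count threshold.

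The cost is a few sentences and a change of procedure, with no extra subjects or data. The downside is a small loss of power where Wald already works: 76% instead of 80% at 10/100,000 and RR 3.7.
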